6.4. Pharmacokinetics

Blood for pharmacokinetic assessments may be obtained by individual needle stick or IV

cannula. If a cannula is used for collection of the whole blood samples, the cannula will be inserted into an arm vein within sufficient time before dosing and may be kept patent using a dilute heparin solution as a flush. An initial volume of approximately 1.0 mL of blood will be collected and discarded prior to collection of each whole blood sample to ensure that the saline or heparin solution does not artificially dilute the samples. If PK samples are collected via individual needle sticks rather than through a cannula, then no extra blood needs to be collected and discarded prior to the collection of the sample.

Each blood sample will be labeled with subject's number, schedule date and time, collection date and time. The actual time of each blood sample will be recorded on the case report form (CRF).

Regimen	Blood sampling	ECG measurements
Regimen 1: Artemether- lumefantrine (AL) Dosing: 0h, 8h, 24 h, 36 h, 48 h, 60 h	 Day 0: Hr. 0 (pre-dose), 0.25, 0.5, 1, 2, 3, 4, 6, 8 (pre-dose), 10, 12, 14 Day 1: Hr. 24 (pre-dose), 26, 28, 30, 36 (pre-dose), 38, 40, 42 Day 2: Hr. 48 (pre-dose), 48.25, 48.5, 49, 50, 51, 52, 54, 56, 60 (pre-dose), 61, 62, 64, 66 Day 3: Hr. 72 Day 4, Day 7, Day 14, Day 28 	Day -1: Hr. 0, 1, 2, 4, 6, 8, 10, 12, 14 Day 0: Hr. 0 (pre-dose), 1, 2, 4, 6, 8 (pre-dose), 10, 12, 14 Day 1: Hr. 24 (pre-dose), 26, 28, 30, 36 (pre-dose), 38, 40, 42 Day 2: Hr. 48 (pre-dose), 49, 50, 52, 54, 60 (pre-dose), 61, 62, 64, 66 Day 3: Hr. 72 Day 4, Day 7, Day 14, Day 21, Day 28
Regimen 2: Amodiaquine (AQ) Dosing: 0h, 8h, 24 h, 36 h, 48 h, 60 h	Day 0: Hr. 0 (pre-dose), 0.25, 0.5, 1, 2, 3, 4, 6, 8 (pre-dose), 10, 12, 14 Day 1: Hr. 24 (pre-dose), 26, 28, 30, 36 (pre-dose), 38, 40, 42 Day 2: Hr. 48 (pre-dose), 48.25, 48.5, 49, 50, 51, 52, 54, 56, 60 (pre-dose), 61, 62, 64, 66 Day 3: Hr. 72 Day 4, Day 7, Day 14, Day 28, Day 42	Day -1: Hr. 0, 1, 2, 4, 6, 8, 10, 12, 14 Day 0: Hr. 0 (pre-dose), 1, 2, 4, 6, 8 (pre-dose), 10, 12, 14 Day 1: Hr. 24 (pre-dose), 26, 28, 30, 36 (pre-dose), 38, 40, 42 Day 2: Hr. 48 (pre-dose), 49, 50, 52, 54, 60 (pre-dose), 61, 62, 64, 66 Day 3: Hr. 72 Day 4, Day 7, Day 14, Day 21, Day 28, Day 35, Day 42

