12.5.2 Safety Analysis

Safety analyses will be based on the safety set. Safety and tolerability of artemether, lumefantrine and amodiaquine will be assessed by comparing the frequency (%) of adverse events and serious adverse events, with particular attention to abdominal pain, appetite perturbation and QT interval prolongation, using the Fisher's exact test. Safety data will be presented in tabular and/or graphical format and summarized descriptively. Any clinically relevant abnormalities or values of potential clinically concern will be described. Subjects will be analysed as treated.

An additional exploratory analysis evaluating independent renal markers against standard blood urea nitrogen/ creatinine levels will be conducted using appropriate statistical methods.

Adverse Events

All adverse event summaries will refer to treatment emergent adverse events, i.e. adverse

events that newly started or increased in intensity after the study drug administration. AE summaries will be generated for all AEs that occurred after study drug administration, until the end of the study.

12.6 Assessment of the relationship between pharmacokinetic parameters and ECG findings.

In addition to the results of the safety analysis, an exploratory analysis of the ECG data will be conducted. The ECG parameters will be compared with the PK properties of the drugs using appropriate statistical methods.

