13.2. Risks

Artemether-lumefantrine

Reported Artemether-lumefantrine side effects have generally been mild. The common side effects are headache (56%), anorexia (40%), dizziness (39%), asthenia (38%), GI disorders (loss of appetite 40%, nausea 26%, vomiting 17%, abdominal pain 17%), arthralgia (34%), myalgia (32%), sleep disorder (22%), palpitations (18%), fatigue (17%). Rare but could be serious side effects are hepatomegaly (9%) and anemia (4%).

Amodiaquine

The main side effects of amodiaquine are nausea, vomiting and fatigue which are mild to moderate in nature. Transient sinus bradycardia and QTc prolongation were reported in malaria patients treated with amodiaquine (16 and 7 of 20 patients, respectively), but did not result in any symptoms (Ngouesse et al., 2001). Transient neurological problems were reported in drug overdose. When the drug was used for a long period such as in malaria prophylaxis (now not recommended), rare adverse reactions of agranulocytosis (1:2000-2200), hepatoxicity (1:15600), yellow pigmentation, and ocular changes including irreversible retinal abnormalities were observed.

Risk of Blood Collection

Sample blood taking may cause some pain, bleeding and bruising. Rarely, a local skin infection may develop. Occasionally, a subject may feel lightheaded or faint when blood is drawn. Blood for the pharmacokinetic study will be drawn via an indwelling catheter whenever possible to minimize the number of venipunctures.

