3.5.3 Safety assessments

The incidence of AEs will be tabulated and reviewed for potential signals and clinical importance. The most prevalent AEs will be reported by group: (AL → AQ → AL + AQ) vs (AQ → AL → AL + AQ). Any Serious Adverse Events (SAEs) including any deaths will also be reported by group. Standard haematological parameters, serum chemistries, liver and renal function test results at screening and post-treatment will be summarised across the treatment groups. For the safety data such as adverse events, proportions will be compared using Fisher's exact test and a significance level of 5% where appropriate.

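### Electrocardiographic change is a secondary endpoint, but the only named test bearing on QT is Fisher's exact test on event frequencies, and the SAP gives no ECG method

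*Protocol*

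**What the plan says.** Protocol 3.2 and SAP 2.4 both list electrocardiographic changes among the secondary safety endpoints. The stated methods are these:

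- **Protocol 12.5.2** compares the frequency of adverse and serious adverse events by Fisher's exact test, "with particular attention to abdominal pain, appetite perturbation and QT interval prolongation". It also promises descriptive tables or graphs, and analysis as treated.
- **Protocol 12.6** adds an exploratory ECG analysis: "The ECG parameters will be compared with the PK properties of the drugs using appropriate statistical methods". It names no QT correction, baseline, model or quantity to be estimated.
- **SAP 3.5.3** covers adverse events, serious adverse events and laboratory results. "The most prevalent AEs will be reported by group", and the two groups are the sequences AL then AQ then AL+AQ, and AQ then AL then AL+AQ. For adverse events and similar data, "proportions will be compared using Fisher's exact test and a significance level of 5% where appropriate". No ECG or QTc method appears, and the 12.6 analysis is not mentioned.

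The data collected are much richer. Protocol 6.3.3 requires triplicate ECGs at each time point. Table 2 in Protocol 6.4 schedules, before every regimen, "Day -1: Hr. 0, 1, 2, 4, 6, 8, 10, 12, 14", followed by ECGs and PK samples through dosing and follow-up.

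**The concern.** The protocol takes QT seriously. Section 13.2 says "Transient sinus bradycardia and QTc prolongation were reported in malaria patients treated with amodiaquine", giving 16 and 7 of 20 patients respectively. Entry requires QTc below 450 ms, and QT has its own criterion for stopping study drug. The safety of co-administration is a secondary objective, so a natural question is how QTc on AL+AQ compares with QTc on each drug alone in the same person.

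The one named test does not answer it. By sequence group, both arms of the comparison contain all three regimens, so a difference between them would reflect order of treatment, not the combination. By regimen, the test ignores that each subject appears under every regimen. Either way, a continuous measurement taken in triplicate is reduced to whether an event was recorded.

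The remaining route, Protocol 12.6, leaves the heart-rate correction, the baseline and the model open in an open-label study. They could therefore be chosen after the data are seen.

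**Working it through.** The plan states no figure for any QT or safety comparison, so there is none to reproduce. Protocol 12.4 justifies 16 subjects only by a cited minimum of 12 for bioequivalence.

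**1. What Fisher's test can detect** (two-sided 5%; sidedness is assumed because neither document states it). With n per group, no events in one group and k in the other, p = 2 × C(n,k) / C(2n,k).

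| Comparison | Result |
|---|---|
| 4/16 v 0/16 | 2 × 1,820 / 35,960 = 0.101 |
| 5/16 v 0/16 | 2 × 4,368 / 201,376 = 0.043 |
| 4/8 v 0/8 | 2 × 70 / 1,820 = 0.077 |
| 5/8 v 0/8 | 2 × 56 / 4,368 = 0.026 |

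So at least five events against none are needed in either layout. If a single drug showed 6/16, close to the 7/20 = 35% cited in Protocol 13.2, the combination would need 13/16 (12/16 gives p=0.073). The 16 v 16 figures are illustrative, because they treat the same subjects as two independent groups. The 8 v 8 layout is the one in SAP 3.5.3.

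**2. What a paired QTc comparison can estimate.** Inputs: n = 16, 15 degrees of freedom, and an assumed SD of the within-subject difference (s) of 8 to 15 ms.

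- 90% CI half-width = t(0.95, 15) × s / √16 = 1.753 × s / 4, which gives 3.5 ms at s = 8 and 6.6 ms at s = 15.
- Difference with 80% power, two-sided 5%, from the noncentral t distribution = 0.749 × s, which gives 6.0 ms at s = 8 and 11.2 ms at s = 15.

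These hold for one contrast at one time point.

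**3. Do the scheduled data support such an analysis?** From Table 2, the same for all three regimens:

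- All 28 ECG times on Days 0 to 3 coincide with one of the 35 PK times. In follow-up, the Day 21 ECG and, where scheduled, the Day 35 ECG have no PK sample.
- Same clock time available on Day -1: Day 0, 9 of 9; Day 1, 6 of 8; Day 2, 7 of 10; Day 3, 1 of 1. The total is 23 of 28. Hours 40, 42, 61, 64 and 66 have no match.

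**4. Is Day -1 free of drug?** Protocol section 1 gives a desethylamodiaquine half-life of 9 to 31 days, and Table 1 a washout of more than six weeks. The fraction of the terminal-phase level left after 42 days is 0.5^(42/9) = 3.9% to 0.5^(42/31) = 39%. After 84 days it is 0.2% to 15%. This concerns Day -1 at Visit 3 in Group B, at Visit 4 in Group A, and to a lesser degree at Visit 4 in Group B. Only the Visit 2 Day -1 is securely drug-free.

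**5. Position of the combination.** Table 1 gives AL+AQ to everyone at Visit 4, so regimen and period cannot be separated for the combination contrasts.

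**The case against.** A reader might infer that no analysis uses the ECGs, that the SAP ignores them, or that the trial cannot estimate a QT effect of the combination. The documents support none of these. Protocol 12.6 commits to an exploratory ECG-PK analysis, and 12.5.2 promises descriptive summaries and analysis as treated. SAP 2.4 lists the endpoint. The design yields the data for a within-subject contrast. What is missing is a specified method. Nor do the documents state a hypothesis of additive QT effect; QT prolongation is the third of three safety topics named in 12.5.2.

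The comparison of sizes is also not like for like: it sets a test on a binary outcome beside a test on a mean, under an SD that the documents do not supply. It shows scale and is not a formal efficiency ratio.

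A baseline-adjusted analysis has difficulties of its own. Some ECG times have no Day -1 match, three of them among the four Day 2 ECGs after the last dose (61, 64 and 66 h; only 62 h matches). Residual desethylamodiaquine may affect later baselines, and the combination always comes last. These points stand. They are reasons to settle the handling in advance, and they do not make the sequence-group comparison informative.

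Finally, this is a secondary endpoint, and the primary PK conclusion is unaffected. That limits the priority of the point.

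**Conclusion.** The point holds as a gap in prespecification together with an unsuitable named test. Carried out as written, SAP 3.5.3 would not contrast the combination with either drug alone, and Fisher's test by regimen would misstate the dependence between regimens. With 16 subjects it needs at least five events against none. A paired QTc analysis of data already scheduled would have 80% power for about 6 to 11 ms and 90% CI half-widths of 3.5 to 6.6 ms.

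The QTc figures rest on the assumed SD of 8 to 15 ms and apply to a single contrast at a single time point. Any estimate for the combination will remain confounded with period, whatever the model. The change should be made; it is not critical to the primary objective.

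**What to change.** Add an ECG section to the SAP:

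1. Average the triplicates and name the QT correction. Choose it on the Visit 2 Day -1 ECGs only; the bradycardia cited in Protocol 13.2 makes this choice matter.
2. Analyse QTc change from the same-clock-time Day -1 value of that period. For hours 40, 42, 61, 64 and 66, state a fallback, such as the mean Day -1 value or the pre-dose value.
3. Fit a mixed model with regimen, time, regimen by time, baseline and sequence as fixed effects and subject as random. Report AL+AQ minus AL and AL+AQ minus AQ with 90% CIs, naming one main time point or summary in advance.
4. State that AL+AQ is always given at Visit 4, so regimen and period are confounded, and that residual desethylamodiaquine may affect later Day -1 values. Add a sensitivity analysis using the Visit 2 Day -1 baseline.
5. Specify the Protocol 12.6 analysis as a linear mixed concentration-QTc model on the paired samples, with lumefantrine, amodiaquine and desethylamodiaquine concentrations.
6. Report QTc outlier counts and adverse events by regimen, as description.

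The cost is SAP text and analysis time. No new subjects, visits, ECGs or blood samples are needed.

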12.7. Interim analyses

No formal interim analysis is planned.

13. STUDY CONDUCT CONSIDERATIONS

13.1. Regulatory and Ethical Considerations, Including the Informed Consent Process

The study will be conducted in accordance with all applicable regulatory requirements. The study will also be conducted in accordance with good clinical practice (GCP), all applicable subject privacy requirements, and, the guiding principles of the Declaration of Helsinki.

13.2. Risks

Artemether-lumefantrine

Reported Artemether-lumefantrine side effects have generally been mild. The common side effects are headache (56%), anorexia (40%), dizziness (39%), asthenia (38%), GI disorders (loss of appetite 40%, nausea 26%, vomiting 17%, abdominal pain 17%), arthralgia (34%), myalgia (32%), sleep disorder (22%), palpitations (18%), fatigue (17%). Rare but could be serious side effects are hepatomegaly (9%) and anemia (4%).

Amodiaquine

The main side effects of amodiaquine are nausea, vomiting and fatigue which are mild to moderate in nature. Transient sinus bradycardia and QTc prolongation were reported in malaria patients treated with amodiaquine (16 and 7 of 20 patients, respectively), but did not result in any symptoms (Ngouesse et al., 2001). Transient neurological problems were reported in drug overdose. When the drug was used for a long period such as in malaria prophylaxis (now not recommended), rare adverse reactions of agranulocytosis (1:2000-2200), hepatoxicity (1:15600), yellow pigmentation, and ocular changes including irreversible retinal abnormalities were observed.

Risk of Blood Collection

Sample blood taking may cause some pain, bleeding and bruising. Rarely, a local skin infection may develop. Occasionally, a subject may feel lightheaded or faint when blood is drawn. Blood for the pharmacokinetic study will be drawn via an indwelling catheter whenever possible to minimize the number of venipunctures.

13.3. Benefit

There are no anticipated direct benefits to the subjects in this study. Knowledge gained from this study is expected to help find the drug dosage for optimal treatment regimen.

13.4. Confidentiality

The information obtained during the conduct of this clinical study is confidential. The results of the research study may be published, but subject names or identities will not be revealed. Records will remain confidential. To maintain confidentiality, the principal investigators at the study site will keep records in locked cabinets and subjects will be only identified by subject number and initial to prevent association with the subject's name.

The monitor(s), the auditor(s), members of the Ethics Committee, and regulatory authorities may be able to access your medical and study records. However, any information is still confidential and your name will not be identified in the publications of this research outcome.

With subject's consent, subject's clinical data and results from blood analyses stored in our database may be shared with other researchers to use in the future. However, the other researchers will not be given any information that could identify the subject.

13.5. Compensation

Subjects will receive compensation for traveling costs associated with traveling to the study site and loss of work time during their stays in the hospital. The amount of compensation will be 500 baht/day for screening visit (visit 1) and each follow up visit after admission visit 2-4 and 6,000 baht for 4 nights admission (visit 2-4). Total compensation will be around 28,000 baht for screening, all admission visits and follow up visits.

If the subject is withdrawn from the study before the study ends, the subject will be compensated for the time that the subject is actually enrolled in the study.

13.6. Data Management

The data collection tool for this study will be approved case report forms (CRFs). Subject data necessary for analysis and reporting will be entered/transmitted into a validated database or data system. Clinical data management will be performed in accordance with applicable standards and data cleaning procedures.

Study records will be stored for a period of 10 years after completion of the study, while electronic data will be retained indefinitely.

13.7. Study Monitoring

The trial will be conducted in compliance with this protocol, International Conference on Harmonization (ICH) Guidelines for Good Clinical Practice (GCP) and any applicable regulatory requirement(s). Monitors will visit the clinical research sites to monitor all aspects of the study in accordance with the appropriate regulations. The objectives of a monitoring visit will be:

1) to verify the prompt reporting of all data points, including reporting SAEs, checking availability of signed informed consent

2) to compare individual subject records and the source documents (supporting data, laboratory specimen records and medical records to include physician progress notes, nurses' notes, subjects' hospital charts)

3) to ensure protection of study subjects, compliance with the protocol, and accuracy and completeness of records

The monitors will be involved with the site initiation visit, study close out visit and interim monitoring visits the number of which will be determined by the quality of the site. In addition, the monitor will inspect the clinical sites regulatory files to ensure that regulatory requirements are being followed. During the monitoring visits, the investigator (and/or designee) and other

study personnel will be available to discuss the study progress and monitoring visit.

13.8. Protocol Deviation and Violation

A protocol deviation is a variance in a research activity between that described in the protocol that has been reviewed and approved by the IRB/EC and the actual activities or procedures that were performed. A protocol deviation may be classified as minor or significant. A "significant" protocol deviation is also referred to as a protocol violation.

Only the site Investigator may institute emergency departures from the protocol that eliminate an apparent immediate hazard to a subject and that is deemed crucial for the safety and wellbeing of that subject. The site IRB/EC must be made aware of these departures from the protocol in accordance with local requirements.

Protocol Deviation

A protocol deviation is an activity performed that deviates from the approved protocol but does not significantly affect the subject's safety and/or efficacy assessment of the trials (no immediate hazard or data falsification). These deviations are to be noted on the "Protocol Deviation /Violation Form" which will be reviewed by the monitor during monitoring visits.

The following are examples of protocol deviations:

- Missed tests or study procedures
- Late or missed visit by a subject.

Protocol Violation

A protocol violation is an activity that has the potential to or is affecting the safety, rights and wellbeing of subjects and/or efficacy assessment of the trial. If a protocol violation is identified by either site staff or the monitor, the site Investigator needs to complete the Protocol Deviation/Violation Form.

The following are some examples of activities that deviate from the protocol that will be considered protocol violations that should be reported:

- Omission or inadequate administration of informed consent form
- Error of study drug administration
- Enrolling a subject who does not meet the study criteria for enrollment
- Subject who developed withdrawal criteria during the study but was not withdrawn
- Any activity that has the potential to or is affecting the subject's rights, safety or welfare

13.9 Insurance Policy

The University of Oxford has a specialist insurance policy in place: - Newline Underwriting Management Ltd, at Lloyd's of London – which would operate in the event of any Subject suffering harm as a result of their involvement in the research."

13.10. Publication Policy

Any data published in the peer-reviewed medical literature will protect the identity of the subjects. This trial will be registered in a web based protocol registration scheme. All those who have made a substantial contribution will be co-authors on publications.

14. RESEARCH USE OF STORED HUMAN SAMPLES/SPECIMENS

14.1. Intended Use of the Samples/Specimens

Samples and data collected under this protocol will be used to study the pharmacokinetic parameters of artemether-lumefantrine and amodiaquine.

14.2. Storage of Samples/Specimens

Samples will be stored no longer than 10 years using codes assigned by the investigators or their designee(s). Access to research samples will be limited using either a locked room or a locked freezer.

In the future, investigators from this protocol and other investigators besides those listed in this protocol may wish to study these samples. A proposal of the planned research will be submitted to the IRB for their consideration.

14.3. Storage of Genetic Sample

Any proposed plans to use this sample other than for the purposes of this study will be submitted to the IRB/EC prior to any genetic testing being performed. Genetic samples will remain in the country of collection until (if applicable) the IRB/EC approves shipment of genetic material for specific testing. A MTA (Material Transfer Agreement) will also be in place before any samples are sent to another institution for testing.

Appendix 1 Protocol Approval and Signature Page

I have read and approve protocol titled A Randomized, **Open-Label Study to Evaluate Potential Pharmacokinetic Interaction of Orally Administered Artemether-lumefantrine and Amodiaquine in Healthy Adult Subjects**. I confirm that this study will be conducted according to all stipulations of the protocol, including all statements regarding confidentiality.

I will conduct this study in accordance with all applicable regulations and Good Clinical Practice (GCP).

(Assistant [name]) Principal Investigator Date

Procedure	Visit 1				Visits 2-4	ļ		
	Screening		Day -1	Day 0	Day 1	Day 2	Day 3	
Informed Consent	×							
Demographics	×							
Medical Hx/ Medication Hx	×		×					
Check in to unit			×					
Physical Exam and symptoms questionnaire	×		×	×	×	×	×	
Vital signs	×		×1	×1	×1	×1	×1	5
Pregnancy test	× ²	-	× ³					9,10,1
ECG	×	lays ¹	× ⁴	× ⁴	× ⁴	×4	×4	3,4,5,6,
Holter monitoring		14 0	×	×	×	×	×	visit
Clinical Lab ⁵ - Hematology - Chemistry - FBS - Urinalysis	×	Within	×				×	Follow up
24-hour urine for creatinine clearance test			×			×		
PK blood collection ⁶				×	×	×	×	
Study Drug Administration ⁷				×	(×)	(×)		
PGx sample ⁸			(×)	(×)	(×)	(×)	(×)	
Adverse event ⁹				×	×	×	×	
Concomitant medication ¹⁰				×	×	×	×	
Discharge from unit							×	

